Statistical methods	A mixed-effect model for repeated measures (MMRM) will be used to obtain adjusted mean changes from baseline for the treatment effects of continuous endpoints. This MMRM model will include fixed effect of treatment as categorical variable, and fixed effect of baseline at each visit as continuous variable. Visit will be considered as repeated measures with an unstructured covariance structure for the within-patient variability. For dose-finding, predicted average response for each dose group and the estimated covariance matrix from the MMRM will be used in the multiple comparison procedures and modelling (MCPMod) analysis. Several possible dose-response patterns will be evaluated in the MCPMod to identify the best-fitting model and optimal dose for further development.

FLOW CHART

Trial Period	Screening	Randomised Run-in Period				Treatment Period								Follow Up Period				
Visit ¹	1 ²	2	3	3.1 Home sampling without visit	4	5 ³	6	7	8	9	9.1 Home sampling without visit	9.2 Home sampling without visit	EoT ⁴	FUp1 ⁵	FUp1.1 Home sampling without visit ²⁷	FUp1.2 Home sampling without visit ²⁷	FUp2 ²⁷	
Visit may be conducted at patient's home ⁶					X		X			X								X
Telemedicine Contact ⁷			X	(X)							(X)	(X)			(X)	(X)		
Weeks (overall)	-11	-8	-4	-2	-1	0	1	2	6	10	12	13	14	15	16	17	18	
Day ²⁹	-77	-56	-28	-14	-7	1	8	15	43	71	85	92	99	106	113	120	127	
Time window for visits (days) ²⁹	Up to 21 days before Visit 2	+/- 2	+/- 2	+/- 2	+ 2	none	+/- 2	+/- 2	+/- 3	+/- 3	+/- 2	+/- 2	+/- 2	+3	+/- 2	+/- 2	+/- 3	
						Pre-dose												
Informed consent ⁸	X																	
Demographics, medical history including historical creatinine data, baseline conditions	X																	
Check of in-/exclusion criteria	X	X				X												
Concomitant therapies	X	X	X		X	X	X	X	X	X			X	X			X	
Height	X																	
Weight	X				X				X				X					
Physical examination	X	X			X				X				X	X				
Vital signs	X	X			X	X	X	X	X	X			X	X			X	
12-lead electrocardiogram (ECG), local assessment ⁹	X					X			X				X	X				
ACTH challenge test ¹⁰	X					(X)	(X)	(X)	(X)	(X)			(X)					
Safety laboratory (blood, urine) ¹¹	X	X			X	X	X	X	X	X			X	X			X	
eGFR ¹²	X	X			X	X	X	X	X	X			X	X			X	

Trial Period	Screening	Randomised Run-in Period				Treatment Period									Follow Up Period				

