		1 ²	2	3	3.1 Home sampling without visit	4	5 ³		6	7	8	9	9.1 Home sampling without visit	9.2 Home sampling without visit	EoT ⁴	FUp1 ⁵	FUp1.1 Home sampling without visit ⁷	FUp1.2 Home sampling without visit ⁷	FUp2 ²⁷
Visit ¹																			
Visit may be conducted at patient's home ⁶					X		X				X								X
Telemedicine Contact ⁷			X	(X)							(X)	(X)				(X)	(X)		
Weeks (overall)	-11	-8	-4	-2	-1	0	1	2	6	10	12	13	14	15	16	17	18		
Day ²⁹	-77	-56	-28	-14	-7	1	8	15	43	71	85	92	99	106	113	120	127		
Time window for visits (days) ²⁹	Up to 21 days before Visit 2	+/- 2	+/- 2	+/- 2	+ 2	none		+/- 2	+/- 2	+/- 3	+/- 3	+/- 2	+/- 2	+/- 2	+3	+/- 2	+/- 2	+/- 3	
						Pre-dose	Post-dose												
Serum cortisol ¹⁴	X					X	X ¹⁵	X	X	X	X			X	X				X
Biomarker sampling (serum, plasma, urine)		X				X				X				X					X
Pharmacogenomic sampling						X ¹⁷													
Optional biobanking sampling (serum, plasma, urine) ¹⁸		X				X			X					X					X
Pregnancy test ¹⁹	X		X			X			X	X				X					X
Spot urine (UACR) ²⁰	X																		
Train patient on FMV and 24-hour urine sampling	X																		
Dispense urine container for FMV urine sampling	X	X			X				X	X	X				X				
UACR First Morning Void ²¹		X		X	X	X			X	X	X	X	X	X		X	X	X	
Dispense urine container for 24-hour urine sampling					X						X								
24-hour urine sample ²¹						X								X					
Paper diary handout ²²		X			X		X	X	X	X	X								
Collect and review paper diary					X	X		X	X	X	X			X					

Trial Period	Screening	Randomised Run-in Period				Treatment Period									Follow Up Period			
Visit ¹	1 ²	2	3	3.1 Home sampling without visit	4	5 ³		6	7	8	9	9.1 Home sampling without visit	9.2 Home sampling without visit	EoT ⁴	FUp1 ⁵	FUp1.1 Home sampling without visit ⁷	FUp1.2 Home sampling without visit ⁷	FUp2 ²⁷
Visit may be conducted at patient's home ⁶					X		X				X							X
Telemedicine Contact ⁷			X	(X)								(X)	(X)			(X)	(X)	
Weeks (overall)	-11	-8	-4	-2	-1	0	1	2	6	10	12	13	14	15	16	17	18	
Day ²⁹	-77	-56	-28	-14	-7	1	8	15	43	71	85	92	99	106	113	120	127	
Time window for visits (days) ²⁹	Up to 21 days before Visit 2	+/- 2	+/- 2	+/- 2	+ 2	none		+/- 2	+/- 2	+/- 3	+/- 3	+/- 2	+/- 2	+/- 2	+3	+/- 2	+/- 2	+/- 3
						Pre-dose	Post-dose											
Randomisation (via IRT)		X				X												
Dispense study drug(s) (via IRT)		X				X		X	X	X								
Administer Empa/ matching placebo during visit ²³		X			X	X	X	X	X	X				X				
Administer BI 690517 / matching placebo during visit						X	X	X	X	X				X				

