2. TRIAL OBJECTIVES AND ENDPOINTS

2.1 MAIN OBJECTIVES, PRIMARY AND SECONDARY ENDPOINTS

2.1.1 Main objectives

The trial will compare 3 doses of BI 690517 with placebo in patients with diabetic and non-diabetic CKD randomised to empagliflozin or placebo as background therapy (established during the randomised run-in).

The trial will characterise the dose-response curve for BI 690517 in patients with diabetic and non-diabetic CKD by assessing 3 doses and placebo. The response is the change from

treatment period baseline in log-transformed UACR measured in First Morning Void urine after 14 weeks. The primary objectives are (1) to demonstrate a non-flat dose response curve, evaluate the quantitative treatment effect size and evaluate the dose-response relationship, (2) to determine an optimal dose of BI 690517 by comparing the change from treatment period baseline in log-transformed UACR measured in First Morning Void urine after 14 weeks between the 3 doses of BI 690517 and placebo.

One set of secondary objectives will be as above but in subpopulations of (1) placebo background therapy (2) empagliflozin background therapy.

These analyses will include all data prior to BI 690517 discontinuation, down-titration of BI 690517, or death, regardless of change in concurrent SGLT2-inhibitor use.

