During the follow-up period the patient will not be treated with trial medication, but should, if possible, continue with any background treatment they are on, and will collect additional urine at home. After the 4-week follow-up period the patient will have a final visit where again blood and urine samples will be collected. With the conclusion of this visit the trial participation is complete for the individual patient.

A rise in serum potassium and a drop in eGFR under treatment with BI 690517 cannot be excluded. Therefore, patients will be monitored closely (weekly for 2 weeks) after starting treatment with BI 690517 or matching placebo, and regularly thereafter.

In order to be able to address future scientific questions, patients will be asked to voluntarily donate biospecimens for banking (please see [section 5.5](#)). If the patient agrees, banked samples may be used for future biomarker research and drug development projects, e.g. to identify patients that are more likely to benefit from a treatment or experience an adverse event (AE), or to gain a mechanistic understanding of drug effects and thereby better match patients with therapies.

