4.2.1.1 Management of serum potassium elevation

Increased potassium levels are not uncommon in patients with CKD and are often multifactorial in nature. A rise in serum potassium under treatment with BI 690517 cannot be excluded and therefore regular measurements of potassium levels are an integral part of the

visit schedule. For any episode of increased potassium level above 5.0 mmol/L, a clinical evaluation should be performed to make individual treatment decisions if a prompt intervention is required. For BI 690517 the dose might be adjusted to keep potassium levels in an acceptable range. The investigator should consider whether a down-titration is appropriate from a clinical perspective considering symptoms, relevant ECG changes, dynamics of potassium changes, intercurrent disorders, and lower ranges of eGFR. For detailed guidance on how to manage serum potassium elevations, please refer to [Table 4.2.1.1: 1](#).

Table 4.2.1.1: 1 Management of serum potassium

Serum Potassium	Actions (BI 690517 / placebo)
< 5.0 mmol/L	Continue on current dose if deemed appropriate (e.g. in absence of clinical symptoms or slow/small increase over time) For clinically relevant serum potassium increases to < 5.0 mmol/L, the investigator may consider interruption and/or down-titration of BI 690517 /placebo.
≥ 5.0 to <5.6 mmol/L	Option 1: Continue on current dose. Recheck K ⁺ within 72 hours. If levels continue to be ≥5.0 mmol/L, either continue dose with weekly monitoring, or follow Option 2 or Option 3. OR Option 2: Down-titration If down titration is deemed appropriate, the BI 690517 / placebo should be temporarily stopped and the next lower dose will be allocated by IRT as soon as possible. After restarting on a lower dose, investigator should recheck K ⁺ within 72 hours. If levels continue to be >5.0 mmol/L, permanently discontinue. OR Option 3: If down titration is considered inappropriate, permanently discontinue BI 690517 / placebo
≥ 5.6-< 6.0 mmol/L	Option 1: Interruption followed by down titration Study medication should be temporarily interrupted. Investigator should recheck K ⁺ every 72 hours and can restart study medication at the next lower dose once K ⁺ falls to < 5.0mmol/L. After restarting on a lower dose, investigator should recheck K ⁺ within 72 hours. If levels continue to be >5.0, permanently discontinue. OR Option 2: If down titration is considered inappropriate permanently discontinue BI 690517 / placebo

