7.2.2 Handling of Intercurrent Events

The expected intercurrent events of interest in this trial are restricted to the Treatment Period and are defined as:

- Premature treatment discontinuation of BI 690517
- Down-titration of BI 690517
- Use of SGLT2i as concomitant medication
- Death

The strategies for handling intercurrent events in this trial are summarised in [Table 7.2.2: 1](#).

Table 7.2.2: 1 Summary of strategies for handling intercurrent events

Estimand strategy	Treatment	Intercurrent event handling
Primary	Randomised treatment	
 - BI 690517 discontinuation: include data prior to study medication discontinuation - Down-titration of BI 690517: include data prior to down-titration - Death: include data prior to death - Use of SGLT2i: include all available data
Supplementary 1	Randomised treatment	
 - BI 690517 discontinuation: include all available data - Down-titration of BI 690517: include all available data - Death: include data prior to death - Use of SGLT2i: include all available data

The primary approach will include all data prior to the intercurrent event, so any data collected after the intercurrent event will be excluded from the primary analysis except for the use of SGLT2i as concomitant medication. Patients will be analysed according to their randomised treatment. The analysis period for the primary approach starts from randomisation to the Treatment Period until either intercurrent event or EoT at week 14, whichever comes first. This approach is analogous to a hypothetical approach with respect to BI 690517.

Supplementary 1 approach will include all data collected even after intercurrent event, except for death. Every attempt will be made to follow up with patients who discontinue treatment prematurely until the end of their planned study participation. Patients will be analysed according to their randomised treatment. The analysis period for the supplementary 1 approach starts from randomisation to the Treatment Period until EoT at week 14. This approach is analogous to the treatment policy approach.

Handling of intercurrent events that are not listed will be decided by blinded review based on the general principle outlined and will be documented in the TSAP.

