6.6.2 Efficacy data

6.6.2.1 Primary endpoint

Missing data for primary analysis will not be imputed:

- If some UACR value(s) at baseline is (/are) missing, all other available UACR samples in week -2, -1, and 0 will be used to derive UACR at baseline.
- If any UACR value after randomisation to the Treatment Period is missing, the missing UACR will not be imputed.
- UACR values excluded from the primary analysis according to the ICEs handling rules will not be imputed.

The Mixed-effect Model for Repeated Measures (MMRM) approach used for the primary endpoint (see [Section 7.4.1](#)) allows for missing data, assuming missing data following the "missing at random" assumption. Even patients with only one post-baseline assessment can be included in the model and can, therefore, contribute to the variance estimation. This primary analysis assumes that patients who had ICE(s) should have behaved similarly to those who remained in the study, and therefore is analogous to the hypothetical estimand strategy.

The table below describes how/when to derive UACR values for the statistical analysis:

Table 6.6.2.1: 1 Principal rule of First Morning Void (FMV) UACR derivation for analysis

	FMV UACR at baseline	FMV UACR at visit 8	FMV UACR at visit 9	FMV UACR at EoT
Derivation	Baseline FMV UACR is defined as the mean of all non-missing assessments from week -2 until prior to the first intake of trial medication BI 690517 or placebo in the Treatment Period.	Average of all available FMV UACR measured at visit 8 (week 6)	Average of all available FMV UACR measured at visit 9 (week 10)	EoT FMV UACR is defined as the mean of all non-missing assessments from week 12 to week 14 (EoT visit)

Sensitivity analyses will be conducted to investigate the potential effect of ICE handling approaches on the results of the primary analysis. Details about implementation of the sensitivity statistical analyses are described in [Section 7.4](#).

[figure not shown]

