7.4 PRIMARY ENDPOINT(S)

7.4.1 Primary analysis of the primary endpoint(s)

The primary analysis of the primary endpoint will be analysed according to the primary strategy of handling ICEs (see [Section 5.1](#)).

Refer to Section 7.2.2 of the CTP for a description of the statistical analysis for the change from baseline in log transformed FMV UACR measured at 14 weeks of trial treatment.

The adjusted mean change in log transformed FMV UACR from baseline at 14 weeks and its standard error will be obtained from MMRM for the placebo and treatment groups. For the MMRM model, derived UACRs at baseline, visit 8, visit 9, and EoT, which were described in [Section 6.6.2.1](#), will be used.

SAS code for **the MMRM model** will be based on the following structure:

```
PROC MIXED DATA=alldat cl method=reml;

CLASS visit trt subject;

MODEL chg = baseline*visit visit*trt stratum / ddfm=kr s CL;

REPEATED visit / subject= subject type=un r rcorr;

LSMEANS visit*trt /pdiff=all om cl alpha=0.05 slice=visit;

RUN;
```

In the event of model non-convergence, the methods described in [Section 10.1](#) will be attempted (in order) to overcome it.

MCPMod Analysis

For the primary analysis the dose-response relationship will be modelled using following doses: placebo, 3mg, 10mg, and 20mg, in combination with empagliflozin or empagliflozin matching placebo, respectively. The multiple comparison procedure will then be implemented using optimal contrast tests which control the family-wise type I error rate at a one-sided $\alpha = 0.05$. For the MCPMod test, the optimal contrasts of each candidate model are calculated using the R-function optCont.

For the final evaluation, the contrast will be provided using the expected model means from the candidate set and the estimated variance-covariance matrix extracted from the MMRM model.

Once the significance of a dose-response signal is established, the dose-response profile and the target dose can be estimated using a model averaging approach for significant models.

To select a dose estimation model out of the set of significant models, estimates for each dose group will be calculated and will be based on the final dose-response model. The choice of the target dose will be based upon efficacy as well as considering safety and other relevant information.

[figure not shown]
The following displays are planned:

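### The primary MMRM leaves out the week-2 UACR that is already collected, and an on-treatment condition in the SAP's FAS shuts some early stoppers out of the supplementary analysis

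*SAP*

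**What the plan says.** **Model visits.** SAP 7.4.1 specifies "For the MMRM model, derived UACRs at baseline, visit 8, visit 9, and EoT". The derivation table in SAP 6.6.2.1 matches: its first post-baseline column is "Average of all available FMV UACR measured at visit 8 (week 6"), and it has no column for Visit 7.

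**Collection.** In the protocol flow chart the row "UACR First Morning Void" is marked at Visit 7 (week 2) and blank at Visit 6. The row "Safety laboratory (blood, urine") is marked at Visits 6, 7 and 8.

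**Data rule.** Protocol 2.1.1 states "These analyses will include all data prior to BI 690517 discontinuation, down-titration of BI 690517, or death". Protocol 7.2.2 states "The primary approach will include all data prior to the intercurrent event", in a period that opens at the second randomisation. The model in protocol 7.2.3 indexes visits but does not name them.

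**Early events.** Under protocol 3.1, "patients will be monitored closely (weekly for 2 weeks) after starting treatment with BI 690517 or matching placebo". If potassium rises, protocol 4.2.1.1 provides for stopping or for down-titration, where "the next lower dose will be allocated by IRT as soon as possible".

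**Analysis set.** Protocol 7.2.1 defines the FAS by one baseline and one post-baseline UACR. SAP 6.3 adds that the post-baseline value must fall while the patient is still on BI 690517, and its Table 6.3:1 assigns the primary endpoint to the FAS alone. SAP section 4 reports no change from the planned analysis. Both documents define a supplementary strategy that keeps every available value after BI 690517 is stopped.

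**The concern.** **(a) Week 2.** The gap falls at a scheduled decision point. A change of dose or a stop prompted by the Visit 7 laboratory result comes after the Visit 7 urine sample and before the Visit 8 one. The patient then has a valid on-treatment UACR response, but the model never sees it. A likelihood analysis under missing at random can adjust for selective loss only through the values it is given. If early events differ by dose and are related to UACR, the EoT means that feed MCPMod shift, while data that would reduce the shift go unused. SAP 6.6.2.1 also says that a patient with a single post-baseline value can be included, which is not so when that value is Visit 7.

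**(b) FAS.** A treatment-policy-type analysis exists to keep people who stop and are followed. Protocol 3.3.4 and 3.3.4.1 ask sites to go on collecting UACR, and patients who stop only one drug to keep attending. An on-treatment entry condition removes some of the people the analysis is meant to represent.

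**Working it through.** **Which sample is left out.** The flow-chart UACR row has 18 cells for 18 visit columns (Visit 5 is split into pre- and post-dose). Treatment-period samples fall at Visits 7, 8, 9, 9.1, 9.2 and EoT. The last three are averaged into the EoT value, and Visits 8 and 9 enter separately. Visit 7 is the only one not used. The separate urine-sampling chart is damaged in extraction near Visit 7, so this rests on the main flow chart.

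**Who is affected.**

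| Patient | Protocol FAS | SAP FAS | Primary MMRM | Supplementary analysis |
|---|---|---|---|---|
| Stopped or down-titrated between Visits 7 and 8 | in | in | no row | in, if later values exist |
| Stops BI 690517 before the first on-treatment UACR, gives later samples | in | out | no usable value either way | out |

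**Assumptions for size.** The documents give no SD and no event rate after the second randomisation.
- SD: solving the MCPMod contrast test (Emax with 80% at 10 mg, exponential with 15% at 10 mg, linear; one-sided 5%) for the powers in protocol 7.5 gives 0.667 (effects 0, 0.10, 0.20, 0.35; 60 per arm; 89.7%) and 0.656 (effects 0, 0.10, 0.16, 0.22; 120 per arm; 83.1%). I use 0.66.
- 120 per arm, 20 mg against placebo, effect 0.22. The SE with complete data is 0.66 × √(2/120) = 0.085.
- Events between weeks 2 and 6: 2% on placebo and 5% or 10% at 20 mg (6 or 12 of 120 patients with no row).
- Log-odds of an event change by b = ±0.7 or ±1.0 per SD of UACR residual. The correlation ρ between week 2 and EoT is 0.5 to 0.7.

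**(a) Approximation, events driven by the week-2 value.** With Visit 7 omitted, |bias| ≈ [p₁/(1−p₁) − p₀/(1−p₀)] × |b| × ρ × SD. This rare-event form runs somewhat high.
- 5%: (0.0526 − 0.0204) × 0.66 = 0.0213. Times 0.7 × 0.5 gives 0.007; times 1.0 × 0.7 gives 0.015.
- 10%: (0.1111 − 0.0204) × 0.66 = 0.0599. The same factors give 0.021 and 0.042.

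**(a) Simulation** (6,000 trials per scenario, unstructured covariance, Monte Carlo SE 0.0011), absolute bias in the EoT difference:

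| Driver of events | Rate at 20 mg | Without Visit 7 | With Visit 7 |
|---|---|---|---|
| Unrelated to UACR | 5%, 10% | the two models differ by at most 0.0003 | |
| Week-2 value | 5% | 0.006-0.012 | at most 0.0024 |
| Week-2 value | 10% | 0.017-0.034 | at most 0.0024 |
| Week-14 value | 5% | 0.012-0.020 | 0.006-0.014 |
| Week-14 value | 10% | 0.034-0.049 | 0.018-0.036 |

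The sign follows the sign of b. Against an SE of 0.085-0.089, the week-2 rows are 0.07 to 0.40 of an SE. Adding Visit 7 removes that bias because events then depend on an observed value. With the week-14 driver it removes only about 23-53%.

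**(a) Parameters.** Three visits: 6 covariance + 3 baseline slopes + 3 × 8 = 24 means + 1 stratum = 34. Four visits: 10 + 4 + 32 + 1 = 47. The difference is 13.

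**(b) Size.** If a share q of the 20 mg arm is left out and would have reverted to placebo level, the treatment-policy difference is overstated by 0.22q. For q = 1% to 5% (1 to 6 of 120 patients) that is 0.0022 to 0.0110.

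**The case against.** **On (a).** A reader might infer that the SAP breaches the protocol. It does not: the sentences on including all data are intercurrent-event rules that say what is dropped after an event, and no protocol text lists the model visits. There is also a plausible reason for starting at week 6, since protocol 3.2 values a stable response late in treatment. That explains keeping week 2 out of the EoT average. It does not explain keeping it out of the model, where visit-specific means and slopes already separate the two.

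The bias needs events that are related to UACR, yet down-titration is for potassium only and the stopping rules rest on potassium, eGFR, cortisol, adverse events and similar grounds. The slopes used are strong: odds change 2.0- to 2.7-fold per SD. Scaling the 5% results linearly to a slope of 0.3 gives 0.006 × 0.3/0.7 ≈ 0.003 to 0.012 × 0.3/1.0 ≈ 0.004, about 0.04 SE. Events prompted by the Visit 6 laboratory are not helped, because no UACR is taken then. SAP 6.7 mentions extended visit windows that are not visible. All of this stands, and it limits the size.

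**On (b).** SAP Table 6.1:1 runs the on-treatment phase to 7 days after the last BI 690517 dose. If the FAS uses that sense, a patient whose last dose is on Day 8 still qualifies with a Day 15 sample, and only about first-week stoppers are lost. Patients who stop both drugs go to an EoT visit and off-treatment follow-up, so the loss falls mainly on those who stop BI 690517 alone. No section on the supplementary model is visible, and SAP text that is not public could name another set. These points narrow (b). They do not reconcile the two FAS definitions or the statement that nothing changed.

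**Conclusion.** **(a)** holds as a cheap improvement. A collected response inside the primary analysis period is unused for patients whose event falls between Visits 7 and 8. The effect is nil if those events are unrelated to UACR and otherwise likely small: 0.006-0.012 log units at an assumed 5% rate, with unknown sign. The larger figures need a 10% rate that the documents do not support. A reader might go on to infer a biased primary result or a loss of power. Neither is shown: the rates, slopes and correlations are assumptions, and no power loss is claimed.

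**(b)** is wrong as written on the visible text, for the supplementary analysis only. The two FAS definitions differ, the difference is undeclared, and the added condition works against a strategy meant to keep data after stopping. The illustrative overstatement is 0.002-0.011 log units and rests on an assumed 1-5% of early stoppers who revert to placebo level. A reader might infer that the primary analysis also loses patients. It does not: these patients have no UACR before the event that the primary strategy could use.

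**What to change.** 1. Add Visit 7 (week 2) to Table 6.6.2.1:1 and enter it as the first post-baseline visit in the MMRM, with visit-specific treatment and baseline effects and inference still at EoT. If Visit 7 stays out, give the reason.
2. For the supplementary analysis, use the protocol's FAS condition (any post-baseline UACR). Keep the on-treatment requirement only as a data-inclusion rule for the primary strategy, and say whether it includes the 7-day residual effect period.
3. Record in SAP section 4 any departure from the protocol that is kept.

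The cost is SAP wording and code, since the data are already scheduled for collection. The model grows from 34 to 47 parameters, so the risk of non-convergence rises slightly. SAP 7.4.1 already plans a fallback for that. Stops and down-titrations that follow the Visit 6 laboratory result remain without a usable UACR.
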